This is a longitudinal, descriptive study evaluating the impact of an educational training for outpatient clinic staff on patient outcomes cared for by the trained staff members. The analyses are complex: 1) there are 2 target groups (staff and patients); and 2) the intervention is offered in 3 stages (teaching; coaching; all-staff education); and it is a pre-post comparison of the impact of a training intervention upon patients cared for by trained staff using 1 site as the control for the other.

The data collected is psycho-social, meaning both psychological and sociological, reflecting graded rather than dichotomous, or Yes-No responses. This means that multiple comparisons are being made. This large array of data requires mathematical modeling to describe true associations and accurate interpretation of the data. This is explained in detail below.

For PATIENTS quantitative results (survey responses) are supplemented by data extracted from the clinical electronic medical record (EMR) and by qualitative interviews with selected participants from each of the 2 target groups.

Addressing AIM 1: STAFF:

QUANTITATIVE: We will use data from Staff-Baseline and Staff-Follow-up surveys at both sites. We will enroll up to 80 STAFF members between the 2 sites. An array of descriptive and graphical techniques will be performed to characterize the distribution of the variables at each point in time as well as aggregate change in work-related stress, or burnout from Baseline (B) to Follow-up (F). Point estimates with confidence intervals will be used to estimate population values. Comparisons of data from participants in the Intervention and Control groups at Baseline (B) will identify potential heterogeneities between sites with regard to the distribution of staff background characteristics that might be related to stress or burnout (e.g., staff's clinic role/position -- physician, nurse, outreach worker, substance abuse counselor, etc.).

Between-group comparisons at B and F will be made with chi-square, t-tests (Fisher's exact as appropriate) and comparisons of change across time will be assessed by paired Student's t-test or paired Wilcoxon test. Post-hoc power calculations will be performed to determine if we have adequate statistical power for further testing.

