Of particular interest would be comparisons between B and F reports of staff burnout (this is a contingency analysis) and HIV-carer stress (paired t-tests). Although some between group comparisons will be made to assess whether the program appeared to impact staff reports of work-related stress, or burnout, analyses of training effect must rely primarily on analysis of individual or subgroup data augmented with insights provided from the qualitative interviews with the Intervention group staff.

The nonrandom assignment of staff, the limited number at each clinic, the nature of CASA training delivery (CASA team receives hands-on training, while remaining staff learn from the CASA team using a train-the-trainer model), and the differential distributions of staff with regard to clinic roles preclude accrual of a sufficient sample size for multivariate analyses to simultaneously control Site and relevant between-group heterogeneities.

Comparisons between sites will be limited to descriptions of findings for two subgroups determined by: 1) whether or not the staff member was part of the CASA Team (Y/N) and, 2) staff's clinic role/position (Physician, Nurse, Outreach, Counselor, etc.). CASA Team members differ from other staff not only because they received hands-

on training in the integration of palliative skills into their role at the clinic, but because they also hold a dual role both as both trainees and trainers. Similarly, the nature and level of potential impact that integrating palliative care precepts into their work is likely to have will vary by the staff member's role at the clinic; not only due to the work they do but on the basis of the clients they serve.

Addressing Aim 2: PATIENTS: Data is collected at baseline (B) and at 2 follow-ups (F) from enrolled patients.

QUANTITATIVE ANALYSIS:

First, descriptive analysis of all data from baseline and 2 follow-ups from each site will be conducted and between-arm comparisons made to understand all study outcomes (clinic attendance, medication adherence, viral suppression, self-esteem, mental health and QOL) and other measures of patients': demographic and psychological characteristics, disease/treatment and health status, psychological history, and goal setting and care planning. These analyses will identify potential heterogeneities of the sample (both within and between arms) that might require statistical redress.

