Descriptive analyses of the training evaluation forms (to be developed following refinement of the curriculum and submitted to the IRB before being used with STAFF) completed by the teaching team or instructors, expert coaches, and HIV clinic staff including administrative staff during all 3 levels of the CASA training including quarterly all-staff educational sessions will be used to evaluate the training. This analysis will 1) confirm that topics and issues intended to be taught were presented including cultural issues; 2) document both consistency and completeness of the training; 3) identify unanticipated issues raised during the training; and 4) identify aspects of the training that need revision or expansion. These descriptive analyses represent what Cook, Cook and Mark (26) refer to as the "take" of the intervention, or how successful the training is at accomplishing what it intends. Participant insights will be used to suggest training revisions to improve the "reach", or scope of the training, success of implementation and overall effectiveness of the training for other settings. The "reach" describes both breadth and depth of the impact of the training. Attendance logs will document that all members of the team received the training.

We will use the RE-AIM framework [62] in analyzing the acceptability, feasibility, and impact of the CASA intervention. The RE-AIM framework focuses on the content and outcome of a training and guides examination of the clinics including the social, cultural, and care needs of the YMSM. The analysis focuses on essential training elements that foster implementation and sustainability of the training incorporating staff and patient perspectives.

LONGITUDINAL DATA ANALYSIS:

The third analysis is longitudinal and will examine trends of change in study outcomes that will describe potential correlates/mediators of change, as well as comparisons of change in study outcomes for both populations (STAFF and PATIENTS) and potential correlates between study arms. Thus we are able to determine training effect and analyze maintenance and sustainability of intervention effects. Assumptions will be checked with non-parametric alternatives. Appropriate multiple testing techniques (i.e., Bonferroni) will be applied as needed. Analyses will be conducted using SAS 9.3 or IBM SPSS Statistics v20.

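### Staff aim: no between-clinic test of change is specified and the sections conflict, so drift shared by both clinics can be read as a training effect

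*Combined protocol and SAP*

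**What the plan says.** Under Sample Size and Data Analysis, question 2, the heading for Aim 1 (staff) plans baseline and follow-up surveys at both sites. Two kinds of test are named. Across clinics: "Between-group comparisons at B and F will be made with chi-square, t-tests". Over time: "comparisons of change across time will be assessed by paired Student's t-test or paired Wilcoxon test". The text then adds that "some between group comparisons will be made to assess whether the program appeared to impact staff reports of work-related stress", but that "analyses of training effect must rely primarily on analysis of individual or subgroup data", supplemented by interviews with intervention-clinic staff.

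The reasons given are non-random assignment, limited numbers, two-tier delivery of the training and unequal role distributions. Together these are said to "preclude accrual of a sufficient sample size for multivariate analyses to simultaneously control Site and relevant between-group heterogeneities". The section continues: "Comparisons between sites will be limited to descriptions of findings for two subgroups determined by" CASA Team membership and clinic role.

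The Longitudinal Data Analysis section of the same answer points the other way. It announces "comparisons of change in study outcomes for both populations (STAFF and PATIENTS) and potential correlates between study arms". The regression with an arm term that follows is written for patients. No equivalent is given for staff.

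**The concern.** A control clinic is useful here because it shows what happens to staff stress over the same period without training. A paired test within the intervention clinic does not use that information. Separate comparisons at baseline and at follow-up do use the control clinic, but neither estimates the difference in change. Under the staff heading, then, no named analysis answers whether stress changed more where staff were trained. The one sentence elsewhere that promises such an analysis has no model behind it.

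Two things are at stake. Change affecting both clinics between the surveys could be credited to the training. And the between-clinic test at follow-up leaves out each person's baseline score, so it carries over any starting difference between the clinics and gives up precision.

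**Working it through.** **The plan's own figure.** There is none to reproduce. The documents give no effect size, SD, dropout or power for staff, and leave power to post-hoc calculation. The enrolment totals agree: 2 × 40 = 80 staff, and 80 + 204 patients = 284.

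**Inputs from the documents**
- Staff number: up to 40 per clinic (sample size section), or up to 25 per clinic completing pre- and post-surveys (Research Design, Phase 5).
- Interval: January/February 2015 to April/May 2016 (Informed Consent Process), which is 14–16 months. Study Procedures gives about 18 months and also 12–18 months.

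**Assumptions.** Two-sided alpha 0.05 and 80% power (the documents state 0.05 and 0.8 for the patient calculation only); baseline–follow-up correlation rho 0.3, 0.5 or 0.7; equal SD at both surveys; no dropout.

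**Step 1: paired test at the intervention clinic, no training effect, drift d = 0.3 SD.** The change score has SD √(2(1−rho)), so the noncentrality is d√n / √(2(1−rho)). The critical t is 2.023 for n = 40 and 2.064 for n = 25.

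| rho | n = 40: noncentrality | Significant | n = 25: noncentrality | Significant |
|---|---|---|---|---|
| 0.3 | 1.604 | 35% | 1.268 | 23% |
| 0.5 | 1.897 | 46% | 1.500 | 30% |
| 0.7 | 2.449 | 67% | 1.936 | 46% |

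The nominal rate is 5%. At n = 40 and rho 0.5, a drift of 0.2 SD gives 24% and one of 0.5 SD gives 87%.

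**Step 2: between-site tests under the same shared drift.** In 5,000 simulated trials (40 per site, rho 0.5, drift 0.3 SD, same baseline distribution at both clinics), rejection rates were 45.6% for the paired test, 5.6% for the between-site test of change and 5.2% for the baseline-adjusted comparison.

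**Step 3: precision.** Detectable difference = (1.960 + 0.842) × s × √(2/n). The factor s is 1 for the follow-up-only test and √(1−rho²) with baseline adjustment. For n = 40, 2.802 × √(2/40) = 0.63 SD. For n = 25, 2.802 × √(2/25) = 0.79 SD.

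| Per site | Follow-up only | Adjusted, rho 0.3 | rho 0.5 | rho 0.7 |
|---|---|---|---|---|
| 40 | 0.63 | 0.60 | 0.54 | 0.45 |
| 25 | 0.79 | 0.76 | 0.69 | 0.57 |

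At 40 per site, power for a 0.5 SD difference is 61% unadjusted and 65%, 73% and 88% adjusted. The gain is small at rho 0.3.

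**Step 4: feasibility.** Site plus baseline score is two terms. A three-level role group makes four, which is 80/4 = 20 staff per term at the cap, or 50/4 = 12.5 at the lower figure.

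**Step 5: limits.** If drift of 0.3 SD occurs at the intervention clinic only (rho 0.6, 40 per site), the adjusted comparison also rejects, about 38% of the time, against 54% for the paired test. If the clinics start D apart and drift equally, the adjusted difference has expectation D − rho·D = (1−rho)D; for D = 0.3 and rho 0.5 that is 0.15 SD, while the difference in mean change is zero.

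**The case against.** The plan is candid. It calls the study descriptive, limits staff inference openly, and gives reasons beyond numbers. CASA Team membership exists only at the intervention clinic, so it cannot be adjusted for across sites, and many role categories could not be modelled alongside site. That stands. It argues against a rich model, not against site plus baseline score, and non-random assignment is a reason to account for baseline.

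Several stronger readings are tempting, and the documents do not support them.
- A reader might infer that a between-site test of change is ruled out. It is not: some between-group comparisons are kept, the clinics are compared at follow-up, and the longitudinal section names the contrast for staff. The defect is conflict and lack of specification.
- A reader might infer that the known disruptions are what the new analysis would remove. The administration changes are reported for the intervention clinic only. The budget cut affected one clinic and is mentioned as the reason for choosing the other as intervention site. The merger of the clinics is undated. None is shown to be a shared change between the two surveys.
- A reader might infer that training would be judged by significance at one clinic and not the other. No section proposes this.
- A reader might infer that baseline scores go unused. The paired tests use them; only the between-site tests do not.

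**Conclusion.** The concern holds in this form: the staff analysis specifies no between-site comparison of change, contradicts itself on whether one will be made, and leans on paired change that cannot distinguish shared drift from training. For a 0.3 SD shared drift, the false-positive rate is 35–67% at 40 staff and 23–46% at 25. The follow-up-only comparison also loses some precision. Correlation and drift are assumptions, since the documents give neither; the direction holds for any non-zero shared drift, and the precision loss for any non-zero correlation.

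A baseline-adjusted comparison deals with shared drift when the clinics start at similar levels. It does not deal with clinic-specific change, and with one non-randomised clinic per arm the result cannot be read as causal.

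**What to change.** 1. Make the main quantitative staff analysis a between-site comparison adjusted for baseline. For stress and other continuous scores, regress the follow-up score on site and baseline score, optionally with a coarse role group, in staff with both surveys. The plan describes burnout as a contingency analysis; if it is analysed in categories, use a logistic or ordinal model of the follow-up category on site and baseline category.
2. Report the adjusted site difference with its confidence interval. Show the difference in mean change beside it, because the two can diverge if the clinics start apart.
3. Keep the paired tests and the CASA Team and role subgroups as description, and align the Aim 1 text with the Longitudinal Data Analysis section.
4. Word the result as a difference between two clinics, and name the intervention clinic's administration changes as a limit.
5. Reconcile who is surveyed twice. The Aim 1 analysis text has both sites; Surveys/Questionnaires gives the staff questionnaires to those receiving the training; Informed Consent Process names both sites and then only intervention-site staff for the two completions. Reconcile also the staff number (25 or 40 per clinic). The comparison needs paired control-clinic data.

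The cost is revised wording, a little extra analysis and one or two degrees of freedom, provided both clinics are surveyed twice. If control staff are not, the comparison cannot be made without adding those surveys.

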The study uses a quasi-experimental design with pre-tests and post-tests for staff being trained. It provides a control group to directly compare the effects of the educational intervention upon the management of patients by measuring responses of patients before and after the staff is, or is not, trained. The Intervention Group (Clinic 1) and Control Group (Clinic 2) are non-randomly assigned. Both clinics agreed and looked forward to participating in the study, but one clinic had significant budget reduction that resulted in selection of the other clinic for the primary intervention. Ideally we would have used a cross-over design offering the intervention to the second site but the funding cycle for this proposal was reduced from 5 to 3 years and it is only feasible to offer one clinic the intervention. However, we intend to offer staff of the control site the palliative training at the end of the study period if the outcomes are shown to be beneficial. We will make a comparison of the two clinics at baseline to identify possible bias in the final analysis of data.

Following is a description of Study activities; at the end, the teaching intervention is described.

ITEMIZED RESEARCH ACTIVITIES: (See Timeline in Additional Documents)

The study is accomplished in 5 active phases with 3 desired outcomes: (A) staff will be able to use coping strategies as they integrate palliative skills with outpatient HIV care and treatment; (B) patients, specifically (YMSM), will be characterized in the era of successful ART with regard to mental health and quality of life; and (C) the curriculum, previously refined in international settings, will be re-adapted for use early in management of chronic illness in the US to engage and retain patients known to be difficult to keep in care.

PHASE 0:

Months 1-6

Usual study start-up activities including finalization of contracts, hiring of personnel, establishment of study offices, creation of the database and purchase of study materials.

PHASE 1: Patient Recruitment and Enrollment

Begins Month 7 of the study and continues through about Month 24.

A. STAFF: No staff are enrolled, taught or interviewed in the first Phase.

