In response to changes in the administration of the intervention site the Delivery Schedule for the intervention was adapted but content was retained: The Educational intervention was a) initiated with an all-staff in-service to introduce aims of the study and one content area; followed by b) 2-hour sessions for the selected CASA Team 1-2 times per month through May, 2015. On-site coaching was reduced to 1 to 2 times per month for 1.25 hours per session. Content was delivered as planned. Because of changes within the intervention clinic itself and lack of space, the "on-site" coaching was held in a familiar space easily accessible by members of the CASA Team. Six quarterly in-services were offered on schedule for all staff.

PATIENTS: There is no intervention for this group but they do complete surveys. Survey responses will be compared between the 2 clinic sites before and after the training intervention. Data is collected at both sites for 9 months prior to the intervention to describe the current YMSM population in Baltimore. Each participant will give informed consent and 1) complete a Baseline Visit at the University of Maryland, Baltimore (UMB) Institute of Human Virology Jacques Initiative Clinic or at the UMB Evelyn Jordan Center where he receives HIV care. Participants will be asked to complete a survey on a password protected touch-pad that will take 45-60 minutes at first completion. The questions are about current health and medical history. This data is encrypted and de-identified before being sent via a secure internet site to our data center at New York University.

Members of the Study Team will review selected data elements from the electronic medical record (laboratory results and diagnoses) that will be compared with survey responses. Personal health information (data) will be extracted, or taken, from the clinical record of enrolled patients to document HIV status relative to clinical management including time in care, medications taken, laboratory results and attendance at clinic visits. 2) Surveys will be questions about health status and symptoms. Participants will be able to listen to the questions read aloud through earphones and a study team member will be present to answer questions.

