Several unadjusted and adjusted Cox Proportional Hazard regression models will be estimated for comparing survival curves between Site 1 and Site 2 including models that allow for time-varying correlates [e.g., Cox-Aalen (97)]. Evidence of a short-term intervention effect on attendance (retention in care) will be made by comparing survival curves at both sites from 8 months (prior to the baseline assessment) to 16 months following the initiation of the intervention training at Site 1. Descriptive analyses and identification of sample heterogeneities and potential sources of bias. Summary statistics and graphical displays will present characteristics of study participants in each intervention arm as reported at B, F1, and F2, as well as to describe aggregate change of time-varying measures over three time periods: B to F1 (short-term gains), B to F2 (longer-term), F1 to F3 (maintenance).

BIAS: Analyses will be conducted to identify potential sources of bias that may require statistical redress in multivariate analyses. Characteristics of participants in the experimental arm at B will be compared to those of patients in the Control group to identify potential heterogeneities between samples. Given the nonrandom assignment of patients to study arm, it will be necessary to compare characteristics of participants in the study arms at B to identify potential heterogeneities between sites with regard to the distributions of patient or other background characteristics that research suggests might be related to patient outcome(s). Characteristics of participants at B will be compared on the basis of their level of study completion (only B, B+F1, or B+F1+F2) to assess attrition and identify its potential correlates. Between-group comparisons within a single interview will be made with chi-square, t-tests (Fisher's exact as appropriate) or one-way ANOVA with F-tests of significance; and comparisons of change across time assessed by paired Student's t-test or paired Wilcoxon test. Concordance between measures at different times will be assessed using correlation coefficients: Pearson or Kendall tau/Spearman. Probit modeling will be used to determine whether specific patient characteristics, stressors, and/or modifiers are associated with attrition.(119) Propensity analyses (93) will be conducted to calculate terms to control for potential unbalance between intervention arms (see "Propensity Scores" below) will be used.

Addressing Aim 3. CURRICULUM:

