o HIV Disease Control Status (unable to initiate therapy; on therapy-HIV controlled; on therapy-HIV not controlled; documented treatment failure; other), viral load suppression (Y/N) [SO]; a dummy variable noting whether the patient was defined as lost-to-follow-up (no contact w/patient > 2 months); and a variable noting persistence of attendance (# of appointments attended in each quarter of the prior year) [SO].

Family History of Substance Abuse 3 questions

o Monthly clinic data for patients will be coded from 6 months prior to accrual into the study until 18 months follow-up.

STAFF Questionnaires are given to the staff who receive the teaching intervention in 2015. There are 2 instruments to measure staff stress related to caring for persons with HIV disease.

2 *Upload a copy of all questionnaires/surveys:

Name	Created	Modified Date
ADDITIONAL questions STAFF.docx	7/21/2016 12:13 PM	7/21/2016 12:13 PM
Staff Questionnaire_v8.26.15. clean copy.doc	8/26/2015 10:18 AM	8/26/2015 10:35 AM
Patient Follow-upSurvey1_v7.7.15	7/7/2015 4:44 PM	7/7/2015 4:44 PM
Patient Total Survey v7.7.15	7/7/2015 4:43 PM	7/7/2015 4:43 PM
Patient Total Survey v5.5.15	5/11/2015 1:27 PM	5/19/2015 11:31 AM
Staff Questionnaire_v11.2014-2.doc	12/1/2014 1:26 PM	12/1/2014 1:26 PM
FINAL_Family History of Substance Abuse (2).docx	10/14/2014 6:57 PM	10/14/2014 6:57 PM
Patient's Total Survey_v6.27.14	7/2/2014 1:02 PM	7/2/2014 1:02 PM
POS_Touch Pad	7/2/2014 1:01 PM	7/2/2014 1:01 PM
Burnout inventory	5/16/2014 1:11 PM	5/16/2014 1:11 PM
AIDS Stress Scale	5/16/2014 1:11 PM	5/16/2014 1:11 PM
FAMCARE Scale.pdf	12/19/2013 4:40 PM	12/19/2013 4:40 PM
Sexual-Behaviors.pdf	12/19/2013 4:39 PM	12/19/2013 4:39 PM
Health Care Power of Attorney.pdf	12/19/2013 4:34 PM	12/19/2013 4:34 PM
POS.pdf	12/19/2013 4:34 PM	12/19/2013 4:34 PM
McGill-QOL.pdf	12/19/2013 4:34 PM	12/19/2013 4:34 PM
Rosenberg Self-Esteem Scale.pdf	12/19/2013 4:34 PM	12/19/2013 4:34 PM
Alcohol-Drug-Use_Mental-Illness.pdf	12/19/2013 4:34 PM	12/19/2013 4:34 PM
Life-Events-Checklist.pdf	12/19/2013 4:33 PM	12/19/2013 4:33 PM
AACTG_Adherence.pdf	12/19/2013 4:33 PM	12/19/2013 4:33 PM
HIV Symptom Index.pdf	12/19/2013 4:33 PM	12/19/2013 4:33 PM
ECOG Performance Status.pdf	12/19/2013 4:32 PM	12/19/2013 4:32 PM
Demographics.pdf	12/19/2013 4:32 PM	12/19/2013 4:32 PM

3 *What is the total length of time that each survey is expected to take?

The STAFF Questionnaires take less than 5 minutes to complete.

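### The retention analysis compares the two clinics but not before with after training, so a standing clinic difference would be read as a training effect or would hide one

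*Combined protocol and SAP*

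**What the plan says.** The Survival Analysis part of Sample Size and Data Analysis (question 2) states: "Several unadjusted and adjusted Cox Proportional Hazard regression models will be estimated for comparing survival curves between Site 1 and Site 2". It allows time-varying correlates. It then says "Evidence of a short-term intervention effect on attendance (retention in care) will be made by comparing survival curves at both sites from 8 months", and the window continues "prior to the baseline assessment) to 16 months following the initiation of the intervention training at Site 1". It names no indicator for training being in force, no site-by-period term and no split of the curves at training start. It does not say what event the curves count.

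The Study Design section states: "The Intervention Group (Clinic 1) and Control Group (Clinic 2) are non-randomly assigned". It gives the reason: "one clinic had significant budget reduction that resulted in selection of the other clinic for the primary intervention". It promises a baseline comparison of the clinics to look for bias. The Data Analysis introduction describes the study as a pre-post comparison in which one site serves as control for the other.

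Pre-training data are planned. Study Procedures (question 1) states: "Data is collected at both sites for 9 months prior to the intervention". Surveys/Questionnaires (question 1) states: "Monthly clinic data for patients will be coded from 6 months prior to accrual into the study until 18 months follow-up".

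**The concern.** Retention in care is a named patient aim, and the hypothesis is that training changes it. A comparison of two clinics answers a different question: whether the clinics differ. In a non-randomised study with one clinic per arm they may well differ without any training. The clinic not chosen had a budget cut, and the plan expects participation of 75% at Site 1 and 55% at Site 2, so the enrolled groups may also be differently selected.

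If Site 1 already kept patients better, the analysis can report a training benefit that does not exist. If Site 1 started worse, a real benefit can be hidden. The pre-training months that would show which case applies are to be collected, but the retention test does not use them as each clinic's own reference.

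**Working it through.** **1. What each contrast estimates.** On the log-hazard or log-odds scale, let *s* be the standing difference (Site 1 minus Site 2), *p* the change over calendar time common to both clinics, and *t* the training effect.

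| | Before training | After training |
|---|---|---|
| Site 2 | a | a + p |
| Site 1 | a + s | a + s + p + t |

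- Site comparison, post-training months only: (a + s + p + t) − (a + p) = **s + t**.
- Site comparison, whole window: roughly **s + w·t**, where *w* is the share of the information that falls after training.
- Change at Site 1 minus change at Site 2: (p + t) − p = **t**.

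The standing difference enters both site-only contrasts in full. The pre-training months dilute *t* but do not cause the bias.

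**2. The plan's own figure.** The sample-size section gives n=140 for the Cox comparison, with no hazard ratio, event rate or event definition, so it cannot be reproduced. Solved backwards with alpha 0.05 (two-sided assumed) and power 0.80, events D = 4(1.96 + 0.84)²/(ln HR)². Then n=140 implies a hazard ratio of 0.42 if 30% have events, 0.51 if 50% do and 0.62 if all do.

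**3. Rejection with no training effect, one case by hand.** Take 85 per site (from the plan) and assume 20% control loss over 12 months, so 1 − 0.80² = 36% over 24 months. Use z = ½√D·|ln HR| and rejection ≈ Φ(z − 1.96).

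| Standing HR | Site 1 retained | D | z | Rejects |
|---|---|---|---|---|
| 0.80 | 0.64^0.80 = 0.700 | 85 × (0.36 + 0.300) = 56 | 0.84 | 13% |
| 0.67 | 0.64^0.67 = 0.742 | 85 × (0.36 + 0.258) = 53 | 1.45 | 31% |
| 0.50 | 0.64^0.50 = 0.800 | 85 × (0.36 + 0.200) = 48 | 2.39 | 67% |

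**4. Range by simulation.** Assumptions: 85-102 per site, entry uniform over Months 7-24 (the planned recruitment period), training at Month 15 (January 2015, since the protocol sets Month 13 at November 2014), window closing 16 months later, 30-50% control loss over 24 months, no training effect. Site-only log-rank test, nominal 5%:

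| Standing HR | At risk from 8 months before entry | At risk from enrolment |
|---|---|---|
| 0.80 | 11-19% | 10-14% |
| 0.67 | 27-46% | 18-34% |
| 0.50 | 57-87% | 40-74% |

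With equal clinics the test rejects in about 5%, as it should.

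**5. Does dropping the pre-training months help?** No. With 16 post-training months only, 85 per site and 20-40% control loss over 12 months, the site-only test still rejects in 10-16% at 0.80 and 52-81% at 0.50.

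**6. Does the before/after contrast help?** On repeated missed-visit events (85 per site, 8 months before and 16 after training), a site-by-period contrast rejects in 4.6-5.8% across standing hazard ratios from 1 to 0.50. A site-only comparison of the same repeated events rejects in 28-38% at 0.80, so richer data make the site-only error worse.

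**7. The planned adjustments.** Propensity terms balance measured patient covariates. A clinic-level feature such as funding is constant within site and cannot be separated from the arm. The time-varying correlates include no named training indicator. The baseline value of the outcome is listed among the terms that the regression models can carry, but the survival section does not repeat it. The baseline clinic comparison describes imbalance without changing the contrast.

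**The case against.** The strongest reply is that the plan intends a before/after comparison. The study is described as pre-post with a control site, the window spans both periods at both clinics, and the longitudinal section plans comparisons of change between arms, with attendance listed among the study outcomes. That intent is credible, and if it is what was meant, a sentence would settle the intention. As written, the trend models are introduced for the outcomes that remain, the before/after site comparison in Study Procedures concerns survey responses, and the retention claim is assigned to the site curves. So it would be wrong to infer that the plan lacks any pre-post design; this test does not carry it out.

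A reader might also infer that including pre-training months is the error. Steps 1 and 5 show otherwise. If the event is one-time loss from care, the months before enrolment can hold few events anyway, because enrolled patients were attending at baseline. That is why the lower ends of the ranges apply in that case.

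A third objection stands: a Cox model with a training-on term is a weak remedy for one-time loss. With risk starting at enrolment and equal clinics, its power is about 7-15%, against 31-59% for the site-only test. The before/after contrast should therefore use repeated attendance.

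**Conclusion.** The concern holds: the retention analysis as written cannot separate training from a standing clinic difference, and none of the planned adjustments removes a clinic-level one. Under the assumptions in step 4, false rejection is about 10-19%, 18-46% and 40-87% at standing hazard ratios of 0.80, 0.67 and 0.50. The standing hazard ratio, loss rate and event are assumptions that the documents do not supply.

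A reader might conclude that the trial will report a false benefit, or that the clinics are known to differ in retention. The documents support neither. They give a reason to expect a difference, not its size or direction, and a standing disadvantage at Site 1 would bias the other way.

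**What to change.** - Base the retention conclusion on repeated monthly or quarterly attendance from the medical record. Use the GEE logit approach already planned, with terms for site, calendar period and site-by-period (training on at Site 1 from the date training starts, off otherwise).
- Report the post/pre change at Site 1 relative to Site 2 with its confidence interval.
- Keep the site survival curves as description only, and do not use a one-time-loss Cox model for this contrast.
- Name the attendance event. The record coding includes a flag for more than two months without contact, but the survival section does not adopt it.
- Reconcile the 8-month look-back in the survival section with the 6 months of pre-accrual coding.
- State how months after the clinics combined (noted under Recruitment and Informed Consent Process) are coded.

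The cost is plan wording and one extra model on data already to be extracted, with possibly some loss of power if the clinics were truly equal before training. With one clinic per arm, the contrast still cannot separate training from other changes specific to one site over time, and the report should say so.
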